The interviewer will introduce themselves and the study using the script in the **In-Person Consent Screen**. If the individual gives consent to learn more after the brief introduction, they will finish the study description and continue with the screening questions, if the individual remains interested. These questions are listed on page two of the **In-Person Consent Screen**. Eligible individuals will be assigned a sequential, unique, non-identifying subject ID#, then go through the consent and enrollment process. The ID#s are assigned at this point because individuals are randomized prior to the recruitment.

2. Consent and enrollment

Written informed consent (see **ICFs**) will be obtained by a trained research staff person who has completed all required Human Subject Protection training via CITI. After reviewing the informed consent form for the group to which the study participant was previously assigned (**See Section 6. Randomization**) and providing potential participants with the purpose of the study, the study's goals, potential risks, and safeguards for confidentiality, participants will be given the opportunity to ask questions and have them answered. Moreover, the interviewer will ask the participant questions to confirm their understanding by asking them to explain in their own words what the study entails, along with the study's goals, main procedures, and risks and benefits (see **Evaluation to Sign a Consent Form for Research**). Only if those able to respond satisfactorily will be asked to sign the informed consent form. Only those still interested in participation will complete this process, others may indicate this at anytime and return to their dormitories.

Other documents to be completed between interviewer and the participant will be to sign a **Release of Information Form** so that the study team can access their START assessments, as well as a detailed **Contact Information Form**.

3. Contact Information and Release of Information Forms

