Within 3-4 days of the baseline interview, the study team will provide a printed copy of each individual's Passport, augmented with detailed information on the referral agencies and resources discussed during the Passport planning meeting.

6. Randomization

Random assignment to the intervention (MEPS) or control conditions will be assigned by recruitment week or month, with all individuals recruited in that time period given the same random assignment. Participants will be given a consent form describing the study arm to which they were assigned and told that their outcomes will be compared to participants receiving a different intervention. The Data Manager will develop a computer-generated list of assignments and provide a new one to the Project Manager at the start of each randomization period. No study team members, other than the Data Manager, will know of this assignment prior to this. This double consent approach has been used by McCusker et al. (1997) to examine the impact of residential substance abuse treatment length on both substance use and HIV risk

behaviors. This approach is selected to minimize dissension and conflict among potential study participants and within the jail dormitories, between those assigned to the study arm that receives incentives and those assigned to the standard-of-care arm.

7. Case-management (Standard-of-Care) intervention arm

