### *Modeling Outcomes.*

Each outcome will be analyzed in longitudinal intention to treat using analyses of all available data from Baseline and 3-, 6-, and 12-month follow-up interviews, mobile app, and abstracted record data on utilization, as appropriate. For PrEP cascade outcomes from aim 1, the model is a logistic generalized linear mixed model (GLMM) with a random intercept for participants and a binary 0-1 outcome with 1 indicating success (screening for PrEP say) and 0 indicating a lack of success (not screening for PrEP). We generally do not expect participants to have any PrEP-related positive outcomes at baseline, and we anticipate using only follow-up data at 3, 6 and 12 months in the analysis of specific Aim 1 outcomes. The fixed effects will be a mean for every date (3, 6, 12 months) for each intervention group, for a total of 9 parameters. The first hypothesis is a test for each outcome of differences at 6 months; secondary tests are for differences at 3 months and at 12 months. If the three groups are different at a given time point, we will do pairwise comparisons among the treatments, particularly between the two intervention arms with and without PMs. Specific Aim 3 is similar, though there may be some participants with appropriate SUDs treatment prior to baseline, thus we will include the baseline observation as part of the outcome. At baseline, groups have not been affected by interventions, thus all groups will be the same, so there is one additional parameter for the baseline mean. Otherwise, the analysis is similar to Aim 1 outcome analyses.

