For specific Aim 2, the question in analyzing outcomes is whether the intensity (mean count) of health care visits per unit time is the same among the three groups. Thus, the analysis is a Poisson GLMM with log link and an offset equal to the log of the time covered by each observation, which models rates of visits per unit time. The advantage of this over binary logit GLMM modeling of 1=yes=had at least one visit in the past three months versus 0=no=no visits past three months, is that the binary model penalizes or rewards participants inappropriately for going a few days longer or shorter than 90 days in between visits. The parameter structure and statistical hypothesis testing is the same as for aim 1, though we estimate rate ratios instead of odds ratios. We will estimate the difference between the desired rate of visits (one per 3 months or per 6 months or per year) and the actual observed rate in each intervention arm.

Initial data analysis includes checking for out-of-range data and data cleaning. We will plot average outcomes and error bars as plus or minus two standard errors of the mean as a function of visit, broken out by intervention arm. These are called empirical summary plots. Weiss (2005) describes our general approach to modeling longitudinal data as will be generated by this study. A GLMM random intercept model can be fit in the SAS software Proc Mixed (Cary, NC 2017); if there are problems fitting the data in Proc Mixed, we will move to Bayesian software such as JAGS in R.

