### *Modeling Issues and Sensitivity Analyses.*

Sensitivity analyses will include predictors that are predictive of missing visits or whose average levels differ across study arms. Predictors predictive of missingness are likely to occur; satisfactory randomization should prevent average predictor levels from differing across intervention groups. We will analyze missing visits as a binary outcome with logistic random intercept regression model as functions of key (baseline; time-fixed) predictors (for example: Baseline behavior (e.g. whether they had tested for HIV in the 3 months prior to baseline), age under 30 vs. 30+; type of SUD; ASAM Level I & II vs. III & IV; stimulant user vs. not; race/ethnicity; preferred substance, education level), prior to performing the final analysis. Variables that are significant predictors of missing visits will be included as predictors in sensitivity analyses of intervention effects. If substantial missingness occurs in key baseline predictors, we will use multiple imputation to fill in the missing predictors. The missing visit analysis omits the baseline time point, as the baseline observation is required. To evaluate randomization, we analyze the key baseline predictors as outcomes in a one-way ANOVA. If some of the predictors differ by intervention arm, they will be included in sensitivity analyses.

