### *Power Calculations.*

For each of the 11 primary outcomes, we calculated power given the Principal Investigator's (PI) estimates of probabilities of success for the 6-month outcomes for each intervention arm. These estimates were based on the existing literature and on preliminary data from the Passport to Wellness study. The PI often specified ranges, in which case we calculated power for the low end and the high end of the ranges resulting in 16 power calculations. Power for the full sample of 399 for testing  $H_0$ : *all arms have the same probability of success*, with a chi-square with 2 degrees of freedom (df) was almost always 1 to three decimal points for alpha=.05; the lowest power was .958 for probabilities of success for the three arms of (0.025, 0.075, 0.15). Some other examples of triples of probabilities we considered were (0.2, 0.6, 0.8), (0.2, 0.45, 0.55), (0.3, 0.5, 0.65). However, we expect a fair amount of loss to follow-up, so we also calculated power for 25% attrition, leaving 100 per group. Again, power is strong, but the lowest power for testing this  $H_0$  is now 86.

Second, we also considered power for comparing between the two intervention groups for testing  $H_0$ : *both intervention arms have the same probability of success*: across a wide range of baseline probabilities, we have 0.8 power at alpha=.05 to detect a difference of 0.17 at n=133, and a difference of 0.20 at n=100 (accounting for loss to follow up) in each group. Because we will be fitting longitudinal models with more data than what goes into a chi-square test, we will have increased power over this basic chi-square test on 2 df.

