### *Multiple Comparisons.*

We have listed 11 primary outcomes at 6 months for the three specific aims. To adjust for multiple comparisons, we propose to use a new methodology proposed in Harwood, Weiss, and Comulada (2017) (HWC17). For n=11 primary outcomes, we expect to reject on average  $0.55 = 11 * 0.05$  null hypotheses, even in the case of no difference between arms. The HWC17 methodology uses a correlated Bernoulli test of  $H_0$ : p=0.05 for n=11 outcomes that rejects the null hypothesis of no effect when 3 or more of the 11 tests are significant at p=0.05. Rejecting this null hypothesis means that the interventions are not the same, gives a type I error of .05, and accommodates correlations across outcomes. We then declare individual outcomes that produced a p-value below 0.05 as significantly different across arms as well. We will separately test outcomes at 3 months, 6 months, and 12 months using this methodology.

1. Weiss RE. *Modeling Longitudinal Data*. 2005 edition ed. Springer; 2005:454.
3. *A language and environment for statistical computing. R Foundation for Statistical Computing*. 2017:ISBN 3-900051-07-0. <http://www.r-project.org/>
4. Rubin DB. Inference and missing data. *Biometrika*. 1976:581-592.

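### Arms are randomised by recruitment week or month, but the SAP's models, balance check and power treat participants as individually randomised, so the stated .05 error rate and power fail if outcomes correlate within a period

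*Protocol*

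**What the plan says.** The protocol, section 6 (Randomization), has arms "assigned by recruitment week or month, with all individuals recruited in that time period given the same random assignment". Section 1 (Recruitment and screening) confirms the order of events: "The ID#s are assigned at this point because individuals are randomized prior to the recruitment". The stated reason is to avoid conflict in the dormitories between people who are offered incentives and people who are not.

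The SAP does not carry this design into the analysis:

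- **Aims 1 and 3** (Modeling Outcomes): for Aim 1, "the model is a logistic generalized linear mixed model (GLMM) with a random intercept for participants"; Aim 3 is handled similarly, with a baseline observation added.
- **Aim 2** is a Poisson mixed model: "The parameter structure and statistical hypothesis testing is the same as for aim 1".
- **Balance check** (Modeling Issues and Sensitivity Analyses): "we analyze the key baseline predictors as outcomes in a one-way ANOVA".
- **Power** (Power Calculations) rests on chi-square tests with 133 or 100 people per group. For the pairwise comparison, "we have 0.8 power at alpha=.05 to detect a difference of 0.17 at n=133, and a difference of 0.20 at n=100".
- **Multiplicity** (Multiple Comparisons): the rule of three or more significant results out of 11 "gives a type I error of .05, and accommodates correlations across outcomes".

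The SAP mentions no term for recruitment period, cluster-robust variance, ICC, design effect or number of periods.

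**The concern.** This is cluster randomisation with the recruitment period as the cluster. A participant random intercept handles repeated visits by one person. It does nothing for the correlation between different people who were recruited in the same week or month and so share an arm.

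Such correlation is plausible here. Peer Mentor availability, case-management staffing and local services can all change over calendar time. So can the working of the jail's advance notice of release, which the protocol (11. Retention) says was not always received in a prior study.

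With any positive within-period correlation, the standard errors of the arm comparison are too small. Each of the 11 primary tests then exceeds its nominal level. The three-of-11 rule takes those tests as inputs and allows for correlation between outcomes, which is a different correlation. Once the rule is met, the SAP also declares individual outcomes significant at .05, so inflation in a single test passes straight through.

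**Working it through.** **Inputs from the documents.** 266 participants in two arms, so 133 per arm if equal (protocol, overview). 25% attrition, leaving 100 per group (SAP, Power Calculations). Alpha .05, 11 primary outcomes, and reject globally if at least 3 are significant (SAP, Multiple Comparisons).

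**Assumptions, because the documents are silent.** Recruitment lasts 12 to 24 months, giving 52 to 104 weekly periods or 12 to 24 monthly periods. The ICC is 0 to .05.

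**Step 1: reproduce the plan's figures without clustering.** For a two-proportion test centred at .5, the difference detectable with 80% power is .171 at 133 per arm and .197 at 100, matching the SAP's .17 and .20. The SAP's lowest three-arm power, .958 for (.025, .075, .15) at 133 per arm, comes out at .942 (simulated Pearson test) to .949 (simulated likelihood-ratio test). The plan's figures are thus independent-person calculations with no hidden allowance for clustering. They belong to a 399-person, three-arm design that the protocol does not have; the pairwise ones carry over only because the number per arm is also 133.

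**Step 2: design effect and true alpha.** With m people per period, DE = 1 + (m − 1) × ICC, and the true two-sided alpha of the unadjusted test is 2 × [1 − Φ(1.96/√DE)]. The detectable difference is computed at n/DE per arm. For all 266:

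| Periods | m | ICC | DE | True alpha | Detectable difference, 133 per arm |
|---|---|---|---|---|---|
| any | any | 0 | 1.00 | .050 | .171 |
| 104 weekly | 2.6 | .01 | 1.02 | .052 | .172 |
| 52 weekly | 5.1 | .05 | 1.21 | .074 | .188 |
| 24 monthly | 11.1 | .01 | 1.10 | .062 | .179 |
| 12 monthly | 22.2 | .05 | 2.06 | .172 | .244 |

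For example, 12 months gives m = 266/12 = 22.17, DE = 1 + 21.17 × .05 = 2.06, 1.96/√2.06 = 1.366, and alpha = .172.

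After 25% attrition (200 analysed) the periods are smaller. For ICC .01 to .05, alpha is .051 to .067 weekly and .059 to .142 monthly. The detectable difference at 100 per arm is .198 to .210 weekly and .204 to .262 monthly.

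**Step 3: simulation of a single test.** Beta-binomial outcomes, success probability .3, 200 people spread unequally over periods, ICC .05, 8000 runs. The individual-level test rejected a true null in .098 of runs with 24 periods and .150 with 12. A t-test on period proportions gave .050 and .055.

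**Step 4: the three-of-11 rule.** With independent outcomes and no clustering, the binomial probability of at least 3 of 11 at .05 is .015. Simulated error with all nulls true, between-outcome correlation 0 to .6:

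| ICC | Weekly | Monthly |
|---|---|---|
| 0 | .015–.054 | .015–.054 |
| .01 | .016–.060 | .025–.084 |
| .05 | .029–.087 | .092–.237 |

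A separate calculation with correlated z statistics agrees in direction. At correlation .4 between outcomes the rule has error .049 without clustering, .083 at DE 1.2, .135 at DE 1.45 and .193 at DE 1.7.

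**Step 5: power.** Take the first and last of the SAP's triples as control and full intervention (an assumption), at 100 per arm. For .025 vs .15, power is .88 without clustering. At ICC .05 it is .84 to .87 weekly and .65 to .77 monthly. For .2 vs .55 it is still .98 at DE 1.78 (12 periods, 200 people).

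**The case against.** The mismatch itself is not open to dispute; its size is. No ICC is given, and some features argue for a small one: everyone comes from one jail unit, wellness plans are individual, and follow-up runs from each person's own release date. Shared calendar time is the only obvious link between people recruited together.

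The larger alpha figures also use all 266 people; after the SAP's own attrition the top of the monthly range is .142, not .172. The three-of-11 rule starts well below .05 when outcomes are independent, so it can stay under .05 despite some clustering. The steepest power loss applies ICC .05 to a 2.5% success rate, which implies a between-period standard deviation of √(.05 × .025 × .975) = .035, or 1.4 times the mean. Most assumed effects are large and survive. Finally, the simulations used simple tests on binary outcomes, not the SAP's mixed models or the Aim 2 counts.

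All of this stands as a limit on magnitude. None of it restores the plan's claims. The protocol leaves the choice between week and month open, so the mild weekly case cannot be presumed. The SAP's remark that longitudinal models add power does not help, because more visits per person do not add randomised periods. And an unknown ICC is a reason to use a method that is valid whatever its value.

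**Conclusion.** The concern holds. The analysis, balance check and power calculation assume individual randomisation, and the trial randomises recruitment periods. That conclusion rests on the text alone.

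The size is conditional on the assumed ICC and number of periods. With weekly periods and an ICC near .01 the effect is minor. With monthly periods and an ICC of .05, a nominal .05 test runs at about .09 to .17, and power for the smallest assumed effect falls well below 80%. The individual-outcome declarations at .05 are inflated at any positive ICC once periods hold more than one person. The global rule's .05 is not guaranteed, though it is not exceeded in every scenario. This must be fixed because it affects every primary test.

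**What to change.** 1. State whether the period is a week or a month, and keep the recruitment-period identifier in the analysis data.
2. Add a random intercept for recruitment period to every mixed model, with degrees of freedom based on the number of periods. Alternatively, obtain p-values by permuting period assignments under the scheme that generated the Data Manager's list. Feed those p-values into the three-of-11 rule, and treat the baseline balance check the same way. Commit to one method before outcomes are seen by arm.
3. Restate power for control versus MEPS with 266 people in two arms, showing a design effect over a stated ICC range (for example 0 to .05) and the expected number of periods.

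The cost is SAP wording, one identifier, and one random effect or a permutation step. The randomisation and sample size are unchanged.

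There is a real price in power if periods are few. A period-level t-test with 12 periods (about 10 degrees of freedom) at ICC .05 has power .61 for .025 vs .15 and .94 for .2 vs .55. The period variance is also poorly estimated: in a check simulation with 200 people and ICC .05, its estimate was zero or negative in 14% of runs with 12 periods and 22 to 30% with 52 to 104, although this matters less when periods are small. With about 12 monthly periods, permutation is the safer choice.

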Information obtained in connection with this study will remain confidential to the extent allowed by law. A code number will be assigned and used to identify participants' study data. A master table linking individuals' study identification (ID) numbers to their personal information will also be maintained in REDCap and accessible only to key members of the investigative team. If outside review occurs, the records will identify only the ID number and not the participant. If the results of this study are presented in a professional meeting or journal, information will be presented so that no individual identifiers will be revealed.

Participants will be encouraged to share as much as they feel comfortable disclosing to their Peer Mentors. Peer Mentors will receive extensive training on maintaining confidentiality and proper professional boundaries while conducting work with participants.

It is possible that the study participants will disclose potentially illegal activities such as the use of illicit substances. This study will apply for an NIH *Certificate of Confidentiality* (COC). The team will use the appropriate wording of the consent for both the COC and the human subjects' requirements. Under law, the privilege of confidentiality, however, does not extend to information about the sexual or physical abuse of a child and/or dependent adult. It is our desire to help report these incidents and/or to work with supportive agencies such as Child or Adult Protective Services. The obligation to report includes alleged or reasonably suspected abuse, as well as known abuse. The PIs and the research team will make every effort to ensure the safety of participants and others throughout implementation. Furthermore, if a participant indicates a desire or plan to harm himself, we will take appropriate steps in order to protect the individual, including contacting the Clinical Supervisor ([name]) or one of the trained counselors with the L.A. CADA Project START team. If none of these individuals is available, the team member will remain with the participant and contact the Suicide Hotline. In the community, Peer

Mentors will also be equipped with emergency referrals to provide where necessary and possible, for resources such as emergency food, housing, domestic violence, and medical/psychiatric care.

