If a serious, emergent risk of harm to a participant or other person is revealed during a participant interaction outside of jail, these steps may involve contacting an emergency response team. If a serious, emergent risk of harm to a participant or other person is revealed in the jail, the START team or study staff will inform the jail-based medical services personnel. Participants will be informed of these exceptions to confidentiality.

16. Potential risks to study participants

Interviewed participants will be subject to minimal risk through their participation, with the greatest risk resulting from potential disclosure of sensitive information that is shared with the study. As indicated above, extensive efforts are planned to minimize this risk. In addition, it is possible that the surveys or Peer Mentor interactions will cause some psychological discomfort, given the sensitive or private information. We will try to limit this by assuring privacy and confidentiality, using well-trained interviewers and Peer Mentors, clarifying the type of questions that will be asked prior to conducting the surveys, and using sufficiently private interview locations. Participants can opt not to answer specific questions.

a. Protection against risks

Participants will be made aware prior to the start of baseline survey that the assessments will include questions on sensitive issues such as sexual risk behaviors, substance use/abuse, and a mental health issues. Participants will be informed about these types of survey questions at the screening and again during the initial informed consent process. Intervention participants who are diagnosed with a sexually transmitted infection or other health condition during the encouraged screenings will receive support from their Peer Mentors in obtaining the follow-up care and treatment that they need.

Participants in the control arm can access the study team for referrals to free services or obtain these from LA CADA.

Interviewed participants will be informed about their rights as research subjects. They may withdraw at any time during the study without penalty or loss. Furthermore, interviewed participants will be told that unless required by law, only the study investigators, members of the project staff, representatives of UCLA Institutional Review Board, National Institutes of Health, and U.S. Office of Human Research Protections will have the authority to review study records. In such cases, they too will be required to

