maintain confidentiality. The data collected will only be accessible to the research team and the Institutional Review Boards. It will be identified via non-identifying subject codes (e.g., sequential identifiers for each site), with the key to other study IDs and names kept in a separate password protected file. Only the local study team members who conduct the follow up interviews will have the information linking individual subjects to these codes. Any paper version of such information collected from the jail will be kept in locked cabinets within locked rooms at the Charles R. Drew University.

We will obtain a Federal Certificate of Confidentiality and maintain the certificate will throughout the life of the research project. We will inform study participants of the above procedures and the limits of confidentiality during the consent process, prior to data collection. Specifically, we will inform participants that criminal behavior (i.e., illicit substance use) is not reported to authorities and that the security of this information is protected by the Federal Certificate of Confidentiality; but we will clarify that information like child abuse and threats of homicide or suicide or in-custody sexual assault (per PREA) will be reported to authorities. Our study survey does not directly assess for suicidal thoughts. However, if these are expressed to study staff during an in-custody interview, the interviewer will report this to jail mental health services who will follow-up with the participant. If this were to occur during an interview outside of jail, the interviewer would assist the respondent in calling the suicide hotline and provide referrals for mental health services.

b. Avoiding potential coercion

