regarding sexual behavior, substance use, mental health, and health conditions. Participants will be informed of the confidentiality of their responses as well as the limits of that confidentiality. They will be informed that sharing any information about the study with others can potentially affect relationships and cause emotional distress to others and self – particularly if this disclosure occurs in custody. Participants will be informed that disclosure of homicide or suicide risk will require notification of the health unit within the jail or, if the participant is outside of jail, referral to appropriate authorities or health care facility for an evaluation by trained mental health experts to determine the best course of action. They will also be informed that conditions of immediate danger or harm may require reporting or notifying appropriate authorities (i.e. the police or the Department of Children and Family Services/DCFS). Participants will be informed that disclosure of violence or victimization relating to someone under the age of 18 or to an elderly adult will require reporting to authorities (i.e., the police or the Department of Children and Family Services/DCFS). Though participants will not be asked about experiences of assault or abuse while incarcerated, we will inform participants that we are required to inform the jail authorities if they do report such incidents. This requirement stems from the Prison Rape Elimination Act.

A determination of the decision-making capacity of the participants will be done prior to obtaining consent and will pay particular attention to participants' understanding of the risks associated with disclosure of information and the implications of that disclosure in accordance with state law. To aid this process, we will use the CDU "**Evaluation to Sign a Consent Form for Research**" with each participant. This asks the interviewer to confirm that the participant is alert and communicative and then has the interviewer ask 4 questions to examine his or her comprehension of the study process. Interviewers will briefly note the answers to each, provide additional teaching as noted and only continue with the interview if the participant is able to communicate acceptable answers to these four questions.

d. Discomfort or distress during the research

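### Protocol sections 15, 16a and 16c disagree on what staff do, and what participants are told will happen, when suicidal thoughts or a wish to self-harm are voiced outside jail

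*Protocol*

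**What the plan says.** Three parts of the protocol deal with self-harm risk outside jail.

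- **Section 15 (Confidentiality)** is not limited to one setting: "if a participant indicates a desire or plan to harm himself, we will take appropriate steps in order to protect the individual". The people it names for this are the Clinical Supervisor and the Project START counselors, and reaching one of them is among the steps listed. The hotline comes next: "If none of these individuals is available, the team member will remain with the participant and contact the Suicide Hotline". The section then turns to serious and emergent risk of harm. Outside jail, "these steps may involve contacting an emergency response team".
- **Section 16a (Protection against risks)** contains both a consent statement and a staff action. Participants are to be told that "threats of homicide or suicide or in-custody sexual assault (per PREA) will be reported to authorities". Shortly afterwards, for suicidal thoughts expressed in an interview outside jail, "the interviewer would assist the respondent in calling the suicide hotline and provide referrals for mental health services".
- **Section 16c (Disclosure of abuse, homicide, or suicide risk)** describes the consent discussion. Participants are to be told, in mandatory terms, that disclosing suicide risk outside jail leads to "referral to appropriate authorities or health care facility for an evaluation by trained mental health experts to determine the best course of action". It adds that immediate danger may lead to notification of authorities.

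**The concern.** A research assistant at a community follow-up interview who hears a participant voice suicidal thoughts can find two instructions. One leads first to a clinically responsible person inside the project. The other leads to a hotline call and a set of referrals. Two staff members could therefore handle the same disclosure differently, each in line with the protocol, and in one case no clinician connected with the study need hear of it.

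Consent is also at stake. Section 16c says the capacity assessment pays particular attention to whether participants understand what follows from disclosing information. That is hard to satisfy when the protocol describes the consequence in two ways and gives interviewers an action that corresponds clearly to neither.

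**Working it through.** No stated figure needs reproducing, and the inconsistency does not depend on arithmetic. The check sets the texts side by side.

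| Place | Addressed to | Trigger | Setting | Response |
|---|---|---|---|---|
| Section 15, self-harm | Study team | Desire or plan to self-harm | Any | Steps including contact with the Clinical Supervisor or a START counselor; if none is available, stay and contact the hotline |
| Section 15, continuation | Study team | Serious, emergent risk | Outside jail | Those steps may extend to an emergency response team |
| Section 16a, staff action | Interviewer | Suicidal thoughts | Interview outside jail | Help the respondent call the hotline; give mental health referrals |
| Section 16a, consent | Participant | Threats of suicide | Not split by setting | Report to authorities |
| Section 16c, consent | Participant | Disclosure of suicide risk | Outside jail | Mandatory referral to authorities or a health care facility for expert evaluation |

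1. **Order of contacts.** In section 15 the hotline follows when the supervisor and counselors cannot be reached. In section 16a it is the interviewer's stated action.
2. **Who is informed.** Section 15 names the supervisor or a counselor. The section 16a staff action names neither.
3. **Consent against staff action.** Section 16a tells participants that threats will be reported to authorities, but its outside-jail staff action contains no report. Section 16c tells participants that referral for evaluation is required. The section 16a action offers mental health referrals without mentioning authorities, a facility or an evaluation.
4. **Consent against consent.** In section 16a a report to authorities is unconditional. In section 16c authorities are one of two routes.
5. **Could the triggers separate the responses?** The terms are thoughts, desire or plan, threats, and risk. The protocol does not define or rank them, gives no threshold between them, and does not cross-reference the sections. Suicide risk in section 16c naturally covers expressed suicidal thoughts, so at least sections 16a and 16c can apply to the same disclosure.

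**Exposure.** The protocol plans 266 participants and three follow-up interviews (3, 6 and 12 months): 266 × 3 = 798 interviews. This is a ceiling on contacts. The SAP power section allows for 25% attrition. If that applied evenly to all three visits (an assumption), 798 × 0.75 = 598.5, or about 599, would remain. Section 9 lowers the count further, because people transferred to prison are not followed and people back in custody are interviewed there. The documents give no disclosure rate, and section 16a notes that the survey does not ask directly about suicidal thoughts. An expected number of events cannot be derived.

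**The case against.** The best defense is that the protocol describes an unlabelled ladder of severity, with thoughts at the bottom, a desire or plan above that, and emergent risk at the top. Part of this stands. Section 15's list is introduced as non-exhaustive. Its sentence on an emergency response team refers back to the steps just described, so it reads as an escalation. A reader might infer that it is a third competing version for the community; the text does not support that.

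Three other stronger readings also fail.

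- A reader might infer that section 16a makes the hotline call and referrals the entire response. It does not say so: nothing there excludes contacting the supervisor, and the same paragraph says threats are reported. Its referrals also overlap in part with the referral in section 16c, so it is not shown that the evaluation would never be arranged.
- A reader might infer that the in-custody routes conflict too. The recipients are named differently, for example "the START team or study staff will inform the jail-based medical services personnel" in section 15, jail mental health services in section 16a and the health unit in section 16c. These may all be the same jail health service, and nothing shows they are rival routes.
- A reader might add Peer Mentor meetings to the exposure. The section 16a sentence is confined to interviewers and interviews, so those meetings fall outside the main inconsistency.

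The ladder still does not rescue the text. If levels were intended they are not written down, and staff cannot apply thresholds that are not stated. Nor does it reconcile the two consent descriptions with the interviewer's action.

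**Conclusion.** The protocol is internally inconsistent on suicidal thoughts or a wish to self-harm voiced outside jail. Sections 15 and 16a differ on the place of the hotline and on whether a supervisor or counselor is contacted. The consent descriptions in sections 16a and 16c differ from the interviewer's stated action and from each other. An interviewer following section 16a to the letter would bypass the section 15 contact and may not do what participants are told will happen.

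The inconsistency touches at most 798 follow-up interviews, and fewer in practice. It has no bearing on sample size, power or type I error; it matters for participant safety and accurate consent. It should be corrected.

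Two assumptions apply. First, suicide risk in section 16c is taken to include expressed suicidal thoughts. Second, what participants are told is taken from the protocol's own account, because the consent forms and training materials were not available for review and may already be clearer. No view is taken on which response is right.

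**What to change.** Reconcile the self-harm text in sections 15, 16a and 16c into one instruction, placed once and cross-referenced from the other sections. Keep the section 15 sentence on serious, emergent risk as the escalation it already is. State which trigger each step applies to, so that thoughts, desire or plan, threats and risk are either distinguished or treated as one. Then align the consent description, the consent forms for both arms, and the interviewer and Peer Mentor training with that instruction, and remove the sentences it replaces. The responsible clinicians should decide the content of each step.

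The cost is a wording amendment to the protocol, matching consent and training text where these differ, and the associated ethics review. The reconciliation itself can rest on roles and services the protocol already names. It changes no sample size, visit schedule or analysis.
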